### **5.1.6 Sensitivity Analysis**

To demonstrate robustness with respect to missing data, a tipping point analysis will be performed for the primary safety endpoint. This will involve imputing all possible combinations of outcomes for the primary endpoint among subjects who terminate the study prematurely without experiencing any primary safety endpoint events.

### **5.1.7 Subgroup Analysis**

Subgroup analyses will be performed to examine the consistency of the primary safety endpoint event rate across subgroups. Subgroups to be examined include, but are not limited to, those defined by achieving >90% of lesions with  $\geq 10$ g contact force, age (both <65 vs  $\geq 65$  and age  $\geq$  median vs < median), sex, and race/ethnicity. Since the number of subjects not achieving >90% lesions with  $\geq 10$ g contact force in this study is likely to be small, the results from similar subjects from the Toccstar IDE study will be pooled with results from this trial. The results for this endpoint will be presented separately for those achieving/not achieving >90% of lesions with  $\geq 10$ g contact force. As needed and appropriate (i.e., for comparison of subgroups), categorical variables will be tested using Fisher's exact test and continuous variables will be tested using two sample t-test. No subgroup specific labeling claims are desired for the primary safety endpoint and no adjustments for multiplicity will be made.

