Treatment for AF includes thromboembolic risk management, heart rate control, and heart rhythm control, which includes cardioversion and catheter ablation. The 2016 ESC AF Guideline indicates that catheter ablation of AF is effective in restoring and maintaining sinus rhythm in patients with symptomatic paroxysmal, persistent, and probably long-standing persistent AF in general as second-line treatment after failure of or intolerance to antiarrhythmic drug therapy. The 2014 AHA/ACC/HRS AF Guidelines, 2016 ESC AF Guidelines, and 2017 HRS/EHRA/ECAS/APHRS/SOLAECE Expert Consensus on AF Ablation all provide a Class I recommendation (Level of Evidence: A) for catheter ablation to maintain sinus rhythm for patients with symptomatic, drug refractory, paroxysmal AF. Contact force sensing ablation catheter systems are a technology that is growing in adoption for AF ablation. These contact force sensing catheter systems provide catheter operators additional feedback by allowing the operator to know how much force is being applied by the catheter tip on the cardiac wall. Recently the 2017 HRS/EHRA/ECAS/APHRS/SOLAECE Expert Consensus on AF Ablation also went on to provide targeted contact force recommendations (Class IIa recommendation, Level of evidence C) during the ablation.

The TactiCath family of catheters has been studied extensively. The early generation TactiCath catheters were investigated in the TOCCATA, EFFICAS I and II, and TOCCASTAR clinical trials. The next generation, TactiCath Quartz, implemented an updated contact force sensing mechanism, which was studied in the TOCCASTAR Supplemental Clinical Study and long-term follow up data are currently being collected in the TactiCath Quartz Post Approval Study (TQPAS). These previous clinical trials have investigated the safety and effectiveness of the previous generations of TactiCath

ablation catheters for the treatment of drug refractory, symptomatic AF. The TactiCath SE ablation catheter is the latest TactiCath contact force sensing catheter from Abbott which incorporates a magnetic sensor for tracking with the EnSite Precision Mapping System and utilizes a new handle and shaft to improve catheter handling.

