## 6 Statistical Considerations

The following section describes the statistical methods for the clinical investigation and justification of the design. Additional details on statistical analyses, including sensitivity analyses, poolability analyses, subgroup analyses and analysis of descriptive endpoint(s) are maintained in a separate Statistical Analysis Plan (SAP).

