### 6.1.1.4 Subgroup Analysis

Subgroup analyses will be performed to examine the consistency of results for the primary safety endpoint. Analysis will be based on Fisher's exact test. No subgroup specific labeling claims are desired for this endpoint and no adjustments for multiplicity will be made. Subgroups to be examined include, but are not limited to, those defined by achieving >90% of lesions with  $\geq 10$ g contact force, age (both <65 vs  $\geq 65$  and age  $\geq$  median vs < median), sex, and race/ethnicity.

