## Statistical Analysis Plan

- AV block
- Cardiac Perforation/Tamponade
- Death
- Diaphragmatic paralysis
- Gastroparesis
- Hospitalization
- Myocardial Infarction
- Pericarditis
- Pneumothorax
- Pulmonary edema
- Pulmonary vein stenosis
- Stroke
- Thromboembolism
- Transient ischemic attack
- Vascular access complication

These events must meet the criteria listed in Appendix C of the CIP to be included in the primary endpoint and will be adjudicated by an independent clinical events committee (CEC). Atrial-esophageal fistula, cardiac perforation/tamponade, and pulmonary vein stenosis that occur >7 days post procedure through 30 days will also contribute to the primary endpoint.

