### 5.1.5 Poolability Analysis

#### 5.1.5.1 Multiple Geography Effect

The trial will be conducted in 35 sites in the United States, Europe and Australia following the same investigational plan and inclusion and exclusion criteria. The trial will be conducted following the same procedures, monitoring plan and training plan in all regions. Poolability of the primary safety endpoint across region (i.e., US vs. OUS) will be evaluated for subjects included in the primary analysis population.

To evaluate the geography effect on the primary safety endpoint, Fisher's exact test will be tested for geography effect in the TactiSense trial against an alpha level of 0.15. If the p-value is less than 0.15, Abbott will examine subject demographics, baseline clinical characteristics for possible correlations and confounding factors.

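### SAP 5.1.7 pools TOCCASTAR subjects into the contact-force safety subgroup without, in the readable text, showing or stratifying results by study

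*SAP*

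**What the plan says.** SAP 5.1.7 plans subgroup analyses to see whether the primary safety event rate is consistent. One subgroup is defined by achieving more than 90% of lesions with at least 10 g of contact force. Expecting few subjects to miss that target, the SAP adds that "the results from similar subjects from the Toccstar IDE study will be pooled with results from this trial". It goes on: "The results for this endpoint will be presented separately for those achieving/not achieving >90% of lesions with" at least 10 g, which is a split by contact force and not by study. Testing is conditional: "As needed and appropriate (i.e., for comparison of subgroups), categorical variables will be tested using Fisher's exact test".

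The external study used another device. Protocol section 2 states: "The early generation TactiCath catheters were investigated in the TOCCATA, EFFICAS I and II, and TOCCASTAR clinical trials". The same section describes TactiCath SE as the latest catheter in the family, with a magnetic sensor and a new handle and shaft.

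Protocol 6.1.1.4 lists the same subgroup and does not mention external data: "Subgroup analyses will be performed to examine the consistency of results for the primary safety endpoint. Analysis will be based on Fisher's exact test". The opening of protocol section 6 leaves such detail to the SAP: "subgroup analyses and analysis of descriptive endpoint(s) are maintained in a separate Statistical Analysis Plan (SAP").

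The poolability checks in SAP 5.1.5 stay inside TactiSense. For region: "Poolability of the primary safety endpoint across region (i.e., US vs. OUS) will be evaluated for subjects included in the primary analysis population". A center check follows in SAP 5.1.5.2.

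**The concern.** The reason given for pooling is the scarcity of subjects who miss the target. The natural reading is therefore that *similar* subjects are TOCCASTAR subjects who also missed it, and that they join only the not-achieving group. The achieving group would then be all TactiSense, while the not-achieving group could be mostly TOCCASTAR, so study is nearly aliased with contact force. Any difference between the studies in catheter generation, operators, period or event ascertainment would enter the contrast as if it were an effect of contact force.

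The error can run either way. A study difference can look like a force effect, or a real signal among low-force TactiSense subjects can be diluted by external subjects at a lower rate. The subgroup exists to show whether the TactiSense safety result is consistent, and a table split only by contact force would not let a reader tell these explanations apart.

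**Working it through.** The documents give no figure for this subgroup: no expected number missing the target, no TOCCASTAR count, no event rates and no power. There is nothing to reproduce, so the check is an illustration.

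**Inputs.** The total of 140 subjects is from SAP 5.6. Everything else is assumed: k = 10 TactiSense subjects missing the target and 130 achieving it; an 8% event rate in TactiSense; m = 30 to 80 TOCCASTAR subjects added to the not-achieving group only; a two-sided level of 0.05.

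**Share of the low-force group from TOCCASTAR.** m/(k+m): 30/40 = 75% to 80/90 = 89%. In the achieving group it is 0%.

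**False difference (no force effect).** The pooled low-force rate is (10 × 0.08 + m × r)/(10 + m), where r is the TOCCASTAR rate, and 8% is subtracted. At r = 12%:
- m = 30: (0.8 + 3.6)/40 = 11.0%, a difference of +3.0 points.
- m = 80: (0.8 + 9.6)/90 = 11.6%, a difference of +3.6 points.

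Rejection probability is the sum of the binomial probabilities of all outcomes for which Fisher's two-sided p is at most 0.05.

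| TOCCASTAR rate | Apparent difference, m = 30 / 80 | Fisher rejection, m = 30 / 80 |
|---|---|---|
| None pooled | 0 | 2.0% |
| 4% | −3.0 / −3.6 points | 3.8% / 13.4% |
| 8% | 0 / 0 | 3.3% / 3.6% |
| 12% | +3.0 / +3.6 points | 8.3% / 12.0% |

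With only 10 subjects added, rejection is at most 4.8%. For other k the difference is ±4 × m/(k+m) points. At m = 80 that is 4 × 80/85 = 3.8 points for k = 5 and 4 × 80/100 = 3.2 points for k = 20. Rejection reaches 12.9% and 11.9% respectively.

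**Masking.** Suppose low-force risk is 20% in TactiSense and 8% everywhere else, a true difference of 12 points.
- m = 30: (2.0 + 2.4)/40 = 11.0%, which shows 3.0 points.
- m = 80: (2.0 + 6.4)/90 = 9.3%, which shows 1.3 points.
- Rejection falls from 20.2% for TactiSense alone to 8.1% and 4.9%.

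**Benefit of pooling.** If TOCCASTAR low-force subjects share the 20% risk, rejection rises from 20.2% to 49% (m = 30) and 70% (m = 80).

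**If TOCCASTAR achievers are pooled too.** With 60 to 100 achievers added and TOCCASTAR at 12% throughout, the unstratified difference shrinks to between 1.3 and 2.3 points and rejection to between 4.6% and 7.9%.

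**What stratification does.** Use Mantel-Haenszel weights n_L × n_A/(n_L + n_A) per study, where n_L and n_A are the low-force and achieving counts. TactiSense has 10 × 130/140 = 9.3. TOCCASTAR runs from 30 × 60/90 = 20.0 to 80 × 100/180 = 44.4.
- If TOCCASTAR runs at 12% in both its groups, each study's difference is 0 and so is the combined one. Study confounding is removed.
- In the masking case the combined difference is 12 × 9.3/(9.3 + 20.0) = 3.8 points down to 12 × 9.3/(9.3 + 44.4) = 2.1 points. Masking is not removed, because TOCCASTAR carries 68% to 83% of the weight.

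**The case against.** The best defense is that the SAP states its reason for pooling in advance and that the reason is sound: a handful of low-force subjects cannot support a useful estimate. If the force effect is the same with both catheters, pooling more than doubles power on the inputs above. If event rates are equal across studies, it causes no inflation. All of this stands, and it is why the fix keeps TOCCASTAR in view. It does not justify omitting the split by study, which costs none of that information.

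A reader might infer that the SAP contradicts protocol 6.1.1.4. It does not. That section is silent on pooling, and protocol section 6 delegates subgroup and poolability detail to the SAP. At most a cross-reference is missing.

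A reader might also infer that TOCCASTAR events were judged to a different standard. SAP 4.1 says of this trial's events: "These events must meet the criteria listed in Appendix C of the CIP to be included in the primary endpoint". Nothing readable says whether TOCCASTAR events were held to that. But protocol 6.1.1 points to further detail on the prior-generation catheter, and the text that follows is redacted, as are SAP 5.1.3 and part of SAP 5.3. The silence carries little weight. For the same reason, a by-study display could exist in text that cannot be read.

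Finally, one might insist that the TactiSense-only result be the main one. That is a preference. The supported request is that it be visible.

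**Conclusion.** The point holds as a minor one. As readable, SAP 5.1.7 combines two studies and two catheter generations, and reports by contact force alone. Study and force are then nearly inseparable if, as seems intended, only the not-achieving group is supplemented. With an assumed four-point difference in rates between the studies, the spurious difference is about 3.0 to 3.6 points. Fisher rejection is 8.3 to 12.0% if TOCCASTAR is higher and 3.8 to 13.4% if it is lower, against 2.0% for TactiSense alone. These figures rest on assumed counts, rates and receiving group. They show that bias is possible, not that it is likely.

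It would be wrong to read this as a threat to the trial's conclusions. The primary population in SAP 5.1.4 contains only subjects who had TactiCath SE inserted, so the test against 16.2% is unaffected. Trial success (SAP 5.7) does not depend on any subgroup, and SAP 5.1.7 and 5.4 disclaim labeling claims and multiplicity adjustment for subgroups. What is affected is the interpretation of one exploratory consistency analysis.

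**What to change.** In SAP 5.1.7, show TactiSense and TOCCASTAR counts and event rates in separate columns, each with exact confidence intervals, for both the achieving and the not-achieving subjects, beside any pooled result. Stratify any combined comparison by study and label it supportive. Add a sentence that stratification removes study-level confounding but not a difference in force effect between catheters.

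The cost is SAP wording and one extra table column. The downside is that the TactiSense-only low-force estimate will look imprecise. One event gives an exact 95% interval of 0.5 to 71.6% among 5 subjects, 0.3 to 44.5% among 10, and 0.1 to 24.9% among 20 (assumed counts). That imprecision exists whether or not it is displayed, and the TOCCASTAR column beside it gives the reader the context that the SAP wanted to supply.

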### **5.1.8 Interim Analysis**

There are no plans for interim analyses for potential early stopping for benefit or for trial or sample size adjustments.

## **5.2 Primary Effectiveness Endpoint**

The performance goal is set at 90% based on experience from previous IDE trials of approved devices relying on pulmonary vein isolation for effectiveness. The hypothesis is formally expressed as:

$$H_0: P < 90\%$$

$H_a: P \geq 90\%$ ,

where P is the percentage of subjects with acute success. The hypothesis will be tested based on a one-sided exact test of binomial proportions at the one-sided 0.05 alpha level. Rejection of the null hypothesis will indicate study success.

### **5.2.1 Analysis Methodology**

The primary effectiveness endpoint event rate will be calculated based on the number of subjects experiencing a primary effectiveness endpoint divided by the total number of subjects in the analysis population. The null hypothesis will be rejected if the lower bound of the one-sided 95% confidence interval for the proportion of subjects in this trial with the primary effectiveness endpoint is greater than 90%.

### **5.2.2 Sample Size**

[REDACTED]

### **5.2.3 Analysis Population**

The analysis population for this endpoint will include enrolled subjects who have also had the TactiCath SE inserted into their vasculature.

### **5.2.4 Subgroup Analysis**

Subgroup analyses will be performed to examine the consistency of results for the primary effectiveness endpoint. Analysis will be based on Fisher's exact test. No subgroup specific labeling claims are desired for this endpoint and no adjustments for multiplicity will be made. Subgroups to be examined include, but are not limited to, those defined by age (both <65 vs  $\geq 65$  and age  $\geq$  median vs < median), sex, and race/ethnicity.

## **5.3 Justification of Clinical Investigation Design**

This is a prospective, multi-center, single-arm clinical trial to demonstrate the acute safety and effectiveness of the TactiCath SE catheter for the treatment of PAF against two performance goals. This clinical investigation will be conducted under an investigational device exemption (IDE) and is intended to support market approval of the TactiCath SE ablation catheter in the United States. [REDACTED]

## **5.4 Adjustment for Multiple Testing**

Both primary endpoints must pass hypothesis testing for the trial to be a success. Descriptive endpoints and subgroup analyses are not intended to support labeling claims. Therefore, multiplicity adjustment is not applicable.

[REDACTED]

## 5.5 Overall Sample Size

[REDACTED]

## 5.6 Timing of Analysis

The primary endpoint analysis will be performed and the pre-market approval (PMA) clinical report will be submitted when 140 subjects have data available to assess the primary safety and effectiveness endpoints.

## 5.7 Trial Success

The trial will be considered successful if the null hypotheses for both the primary safety and effectiveness endpoints are rejected.

## 5.8 Interim Analysis

No interim analysis is planned for this clinical investigation.

## 5.9 Statistical Criteria for Termination

There are no statistical criteria for termination of this clinical investigation.

## 6 DESCRIPTIVE ENDPOINTS AND ADDITIONAL DATA

Ten descriptive endpoints will be summarized for completeness and supportive information.

### 6.1 Descriptive Endpoint #1:

Descriptive endpoint #1 is ablation data collected during the procedure, including:

- Power
- Temperature
- Irrigation flow rate
- Contact force
- Procedure time
- Total ablation time
- Total fluoroscopy time
- Total RF application time
- Usage of Automark

#### 6.1.1 Analysis Methodology

Descriptive statistics will be generated for all variables.

#### 6.1.2 Analysis Population

The analysis population for this endpoint will include all enrolled subjects who have also had the TactiCath SE inserted into their vasculature and radiofrequency energy was delivered.

[REDACTED]

## 6.2 Descriptive Endpoint #2:

Descriptive endpoint #2 is the proportion of index cases achieving  $\geq 90\%$  lesions with  $\geq 10\text{g}$  contact force. Corresponding exact two-sided 95% binomial confidence intervals will also be calculated.

### 6.2.1 Analysis Methodology

Subjects with at least 90% of lesions with  $\geq 10\text{g}$  achieved will be divided by the analysis population. Corresponding exact two-sided 95% binomial confidence intervals will also be calculated.

### 6.2.2 Analysis Population

The analysis population for this endpoint will include all enrolled subjects who have also had the TactiCath SE inserted into their vasculature and radiofrequency energy was delivered.

## 6.3 Descriptive Endpoint #3:

Descriptive endpoint 3 is defined as serious adverse events and adverse events related the device and/or ablation catheter through 30 days post ablation.

### 6.3.1 Analysis Methodology

The number and percentage of subjects experiencing adverse events will be summarized, by seriousness and relatedness. Corresponding exact two-sided 95% binomial confidence intervals will also be calculated. Subjects who terminate the study prematurely without experiencing any adverse events through 30 days post ablation will not be considered as having any events for this analysis.

### 6.3.2 Analysis Population

The analysis population for this endpoint will include all enrolled subjects who have also had the TactiCath SE inserted into their vasculature.

## 6.4 Descriptive Endpoint #4:

Descriptive endpoint 4 is defined as serious adverse events and adverse events related the device and/or ablation catheter through 1 year post ablation.

### 6.4.1 Analysis Methodology

The number and percentage of subjects experiencing adverse events will be summarized, by seriousness and relatedness. Corresponding exact two-sided 95% binomial confidence intervals will also be calculated. Subjects who terminate the study prematurely without experiencing any adverse events through 1 year post ablation will not be considered as having any events for this analysis.

### 6.4.2 Analysis Population

The analysis population for this endpoint will include all enrolled subjects who have also had the TactiCath SE inserted into their vasculature.

## 6.5 Descriptive Endpoint #5

Descriptive endpoint #5 is one-year success, defined as freedom from symptomatic AF/AFL/AT lasting at least 30 seconds without a new Class I or III AAD or a higher dosage of pre-existing AAD as assessed from the end of the 3-month blanking period to 12 months following the ablation procedure.

A full 10-second 12-lead ECG recording may also count as a failure unless there is evidence that the recorded arrhythmia is short-lived and less than 30 seconds.

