##### 3-Month (90 ± 14 days), 6-Month (183 ± 21 days), 12-Month (365 ± 21 days) Follow-up

- Complete QOL (EQ-5D-5L & AFEQT)
- 12-lead ECG
- 24-hour Holter monitor at the 12-Month Follow-up
- Document adverse events and protocol deviations.
- Document AAD and anti-coagulant usage.
- If there are symptoms present that suggest pulmonary vein stenosis (e.g. shortness of breath, cough, and hemoptysis), complete CT or MRI imaging of pulmonary veins.
- Provide subject a trans telephonic monitor to record monthly heart rhythm and symptomatic episodes during follow up from 3 to 12 months.

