#### 5.3.5 Re-ablation Procedure and Anti-Arrhythmic Drug Usage

Subjects may be re-treated with ablation up to two times during the 90-day blanking period between days 31 and 80 after the index procedure. Re-ablation cannot be performed within 30 days of the latest ablation procedure. Re-treatment during this interval will not constitute a treatment failure and must be performed with the TactiCath SE catheter. Re-ablation per standard of care after the blanking period may be performed if recurrence is detected using any commercially available catheter. This will be counted as a treatment failure.

During the blanking period, it is recommended that any current antiarrhythmic medication be continued following the ablation procedure. Current AADs should be withdrawn 4-6 weeks after ablation, unless clinically contraindicated to assess for recurrence of symptoms and the necessity for re-ablation during the blanking period.

If documented symptomatic AF recurs during the 3-month blanking period and the patient requires antiarrhythmic drug therapy, a previously ineffective but tolerated antiarrhythmic drug may be re-initiated to allow for the assessment of its effectiveness when combined with ablation.

All Class I and Class III AADs will be discontinued at the end of the blanking period. Beta-blockers, calcium channel blockers or digitalis may be used during the 9-month chronic effectiveness assessment period if prescribed for reasons unrelated to arrhythmia management. Subjects are encouraged to continue their use through the end of the study unless it is determined to be unnecessary or detrimental by the investigator. Subjects who experience a recurrence of symptomatic PAF after the blanking period (treatment failure) should retry a previously failed AAD before a new medication is prescribed to evaluate the effectiveness of combined ablation and drug therapy.

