### 5.9 Core Lab

A core lab will be used for the collection, interpretation, and collation of data collected from the following procedures:

- Trans telephonic monitoring (TTM)
- 24-hour Holter monitoring
- 12-lead ECG

The core lab will provide independent review of this data by appropriately trained personnel using standardized procedures to interpret TTM, 24-hour holter and 12-lead ECG tracings and adjudicate atrial arrhythmias. Findings will be communicated to the investigator and the sponsor.

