### 6.5.1 Analysis Methodology

Freedom from AF will be calculated as the number of subjects without a failure as defined in section 6.5 divided by the total number of subjects in the analysis population. Corresponding exact two-sided 95% binomial confidence intervals will also be calculated.

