## 6.6 Descriptive Endpoint #6

Descriptive endpoint #6 is one-year drug-free success, defined as freedom from any AF/AFL/AT lasting at least 30 seconds or any Class I or III AAD after removal from antiarrhythmic drug therapy as assessed from the end of the 3-month blanking period to 12 months following the ablation procedure.

A full 10-second 12-lead ECG recording of arrhythmia may be substituted for a 30-second recording unless there is evidence that the recorded arrhythmia is short-lived and less than 30 seconds.

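### Re-ablation after the blanking period is a treatment failure in the protocol, but descriptive endpoint #5 (and, with less effect, #6) does not list it as a failure

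*SAP*

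**What the plan says.** - **Re-ablation.** Protocol 5.3.5 permits re-ablation after the blanking period when a recurrence is detected, "using any commercially available catheter. This will be counted as a treatment failure". It does not require that recurrence to be symptomatic or to last a minimum time. The section gives the same label to a second event: "Subjects who experience a recurrence of symptomatic PAF after the blanking period (treatment failure", the label standing in parentheses.
- **Endpoint #5.** Protocol 4.3.3 and 6.1.7 and SAP 4.3 and 6.5 give one definition: "freedom from symptomatic AF/AFL/AT lasting at least 30 seconds without a new Class I or III AAD", with a higher dose of an existing antiarrhythmic drug (AAD) as the remaining failing event. SAP 6.5.1 sets the result as "the number of subjects without a failure as defined in section 6.5 divided by the total number of subjects in the analysis population".
- **Endpoint #6.** Protocol 6.1.8 and SAP 6.6 require "freedom from any AF/AFL/AT lasting at least 30 seconds" and from any Class I or III AAD. Re-ablation is not named here either.
- **Detection.** Protocol 5.3.4 says: "Provide subject a trans telephonic monitor to record monthly heart rhythm and symptomatic episodes during follow up from 3 to 12 months". It also schedules 12-lead ECGs at 3, 6 and 12 months. On core laboratory readings, Protocol 5.9 says: "Findings will be communicated to the investigator and the sponsor".
- **Timing.** Protocol Appendix B sets blanking at 90 days. Protocol 5.3.5 exempts re-treatment on days 31 to 80 from being a failure.
- **Endpoints #3 and #4.** The lists in Protocol 4.3.3 and SAP 4.3 cover adverse events related to the procedure or the ablation catheter. The analysis sections (Protocol 6.1.5 and 6.1.6; SAP 6.3 and 6.4) name the device or the ablation catheter and leave out the procedure.

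**The concern.** The protocol says how post-blanking re-ablation is to be counted, but the analysis definition gives no means of counting it. SAP 6.5.1 refers back to a closed list, so a programmer following the SAP would leave such a subject among the successes, while a reader of Protocol 5.3.5 would expect a failure. Endpoints #5 and #6 are the trial's only 12-month rhythm outcomes. If the gap stays open, the classification will be settled after the data are seen.

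The #3/#4 mismatch is a similar drafting problem. Read literally, the analysis wording drops non-serious events related only to the procedure. It drops serious ones too if the relatedness condition is taken to apply to both.

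**Working it through.** **Step 1. The texts side by side.** Events are after day 90 and each subject is then re-ablated:

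| What led to re-ablation | Protocol 5.3.5 | #5 | #6 |
|---|---|---|---|
| Symptomatic AF/AFL/AT of at least 30 s | failure | failure | failure |
| Recurrence with a new Class I or III AAD | failure | failure | failure |
| Asymptomatic episode of at least 30 s, no AAD trigger | failure | **success** | failure |
| Recurrence not documented at 30 s, no AAD trigger | failure | **success** | **success** |

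The definitions part from the protocol in the last two rows for #5 and in the last row only for #6.

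**Step 2. Can these rows occur?** Monthly transtelephonic recordings between 3 and 12 months, and the 3- and 6-month ECGs, can show a rhythm the subject did not feel. The core laboratory reports it to the investigator, and Protocol 5.3.5 asks only that a recurrence be detected. The route exists. The documents give no basis for saying how often it would be used.

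**Step 3. Size for #5.** The plan states no expected rate for #5, so there is no figure to reproduce. As a working denominator I take the 140 subjects of SAP 5.6; this is an assumption.

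- Shift per affected subject = 1/N. At N = 140: 1/140 = 0.71 points. At all 156 enrolled: 1/156 = 0.64 points.
- If early leavers shrink the denominator to about 127 or 115 (see Step 4), the shift is 0.78 or 0.87 points.
- From an assumed 105/140, with exact two-sided 95% intervals:

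| Subjects reclassified | Success | 95% CI |
|---|---|---|
| 0 | 105/140 = 75.0% | 67.0-81.9% |
| 2 | 103/140 = 73.6% | 65.5-80.7% |
| 4 | 101/140 = 72.1% | 63.9-79.4% |

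**Step 4. Early leavers (optional reporting only).** SAP 6.5.2 and 6.6.2 keep a subject without the 1-year visit only if that subject failed. Assume true success S = 75%, a constant failure hazard from day 90 to day 365, and a share d leaving uniformly over days 0-365, independently of outcome. The chance of being event-free at exit is e = 90/365 + (275/365) × 0.25/(-ln 0.75) = 0.901.

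- Denominator: 140 × (1 - d × e) = 127.4 at d = 10% and 114.8 at d = 20%.
- Reported success: (1 - d)S / [(1 - d) + d(1 - e)] = 74.6%, 74.2% and 73.2% at d = 5%, 10% and 20%.
- All leavers fail, to all event-free leavers succeed: (1 - d)S to (1 - d)S + d × e = 67.5-76.5% at 10% and 60.0-78.0% at 20%.

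**Step 5. Endpoints #3 and #4.** Each subject whose only event is related to the procedure alone moves the rate by 1/140 = 0.71 points if the analysis wording is followed literally.

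**The case against.** **Protocol 5.3.5 names no endpoint.** This is true, and Appendix B does not define treatment failure. One fair reading is that re-ablation follows a recurrence the endpoints already capture, and for most subjects it would. But the section requires neither symptoms nor duration, and it applies the same label to symptomatic recurrence, which #5 does count. It would go too far to say that #5 breaches a rule written for #5. What stands is that a stated counting rule has no counterpart in the analysis.

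**The event may never happen.** This stands too. Re-ablation without symptoms or a drug change may be rare or absent.

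**A reader might infer that the 12-month Holter is a main route.** Protocol 5.3.4 places the "24-hour Holter monitor at the 12-Month Follow-up", participation ends with that visit (Protocol 5.6), and #5 is assessed only to 12 months. A re-ablation prompted by it would in practice fall after exit, so the documents do not support that route.

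**SAP 6.5 says a full 10-second ECG may also count as a failure.** Read loosely, this would catch a silent ECG finding. Protocol 6.1.7 and the note in SAP 4.3 let the ECG replace only the 30-second recording and do not waive the symptom condition. Even on the loose reading, the transtelephonic route remains open.

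**Days 81-90 lie before the #5 window.** Correct, so one clarifying sentence is enough.

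**A reader might infer that the #5/#6 population rule is an error calling for Kaplan-Meier.** Under the Step 4 model it lowers success by only 0.4 to 1.8 points. Kaplan-Meier is not uniformly better. If the failure hazard doubles after exit, the planned proportion is off by +0.4/+0.6 points at 10%/20% dropout and Kaplan-Meier by +1.2/+2.4. If it halves, they are off by -1.5/-3.2 and -0.7/-1.4. SAP 6.13 already summarises withdrawals. This is a reporting preference.

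**The #3/#4 mismatch is a slip.** Agreed: the endpoint lists, and Protocol 8.2, which collects events related to catheter or procedure, show the intent. It still needs correcting.

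**Conclusion.** The point holds and is minor. Protocol 5.3.5 counts post-blanking re-ablation as a failure; the #5 definition and its counting rule do not, and #6 shares the gap to a smaller extent. The result can be wrong only for a subject re-ablated without a qualifying recurrence or AAD change. Each one is worth about 0.7 points of #5 at an assumed 140 analysed, against an exact interval about 15 points wide (67.0-81.9% at an assumed 105/140). The number affected cannot be known from the documents and may be zero.

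A reader might infer that #5 will be materially overstated, or that #6 needs no change. The documents support neither: nothing indicates how many subjects are affected, and #6 omits the event as well. These endpoints are untested (SAP 4.3), support no labelling claim (SAP 5.4) and do not enter trial success (SAP 5.7). The #3/#4 wording mismatch is a real drafting error.

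**What to change.** 1. Reconcile Protocol 5.3.5 with the #5 and #6 definitions (Protocol 4.3.3, 6.1.7, 6.1.8; SAP 4.3, 6.5, 6.6) so that the analysis counts post-blanking re-ablation as a failure, as the protocol states. Report the number of subjects re-ablated.
2. State how the analysis classifies any re-ablation on days 81-90. This concerns classification only; no clinical rule changes.
3. Correct the #3/#4 wording in Protocol 6.1.5 and 6.1.6 and SAP 6.3 and 6.4 to match the endpoint list, so that events related only to the procedure are included.
4. Optional: for #5 and #6, show the number excluded for lack of a 1-year visit, with a best/worst-case range. Beside #4, show the number still followed at 1 year, since SAP 6.4.1 counts event-free early leavers as having no event.

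Cost: a few sentences and, if item 4 is taken up, a few simple counts. All planned analyses stay, and sample size, primary endpoints and the success rule are unaffected. Reported #5 success may be slightly lower.
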